9. APPENDICES

Appendix 1. Summary of Efficacy Analyses

Endpoint	Analysis Type	Population	Data Inclusion and Rules for Handling Intercurrent Events and Missing Data	Analysis Model
Change from baseline to Month 12 in mean standing height	Summary	FAS	Separately for observed data and imputed data.	N/A
	Main analysis	FAS	All data collected will be included regardless of intercurrent events. Missing data will not be imputed.	MMRM with terms time,dose, gender & age
	Sensitivity/supplementary analysis	PPAS	All data collected will be included regardless of intercurrent events. Missing data will not be imputed.	ANOVA
Change from baseline to Month 12 in mean arm span-height difference	Summary	FAS	Separately for observed data and imputed data.	N/A
	Main analysis	FAS	All data collected will be included regardless of intercurrent events. Missing data will be not be imputed.	MMRM with terms time,dose, gender & age
	Sensitivity/supplementary analysis	PPAS	All data collected will be included regardless of intercurrent events. Missing data will not be imputed.	ANOVA

Appendix 2. Data Derivation Details

Appendix 2.1. Definition and Use of Visit Windows in Reporting

Visit Label	Target Day	Start Day	End Day
Screening	NA	Day -14	Day -1
Day 1	Day 1	Day 1	Day 1
Day 4	Day 4	Day 2	Day 6
Day 8	Day 8	Day 7	Day 9
Day 15	Day 15	Day 10	Day 19
Day 29	Day 29	Day 20	Day 39
Month 2	Day 61	Day 40	Day 75
Month 3	Day 91	Day 76	Day 105
Month 4	Day 121	Day 106	Day 135
Month 5	Day 151	Day 136	Day 165
Month 6	Day 181	Day 166	Day 195
Month 7	Day 211	Day 196	Day 225
Month 8	Day 241	Day 226	Day 255
Month 9	Day 271	Day 256	Day 285
Month 10	Day 301	Day 286	Day 315
Month 11	Day 331	Day 316	Day 345
Month 12	Day 365	Day 346	Day 366

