9.4. Statistical Analyses

The SAP will be developed and finalized before database lock and will describe the analyses and procedures for accounting for missing, unused, and spurious data. This section is a summary of the planned statistical analyses of the primary and secondary endpoints.

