4. ANALYSIS SETS (POPULATIONS FOR ANALYSIS)

Data for all participants will be assessed to determine if participants meet the criteria for inclusion in each analysis population prior to unblinding and releasing the database and classifications will be documented per standard operating procedures.

Population	Description
Full Analysis Set (FAS)/Safety	All participants receiving at least one dose of reciferecept. Participants will be analyzed according to the dose they actually received.
Per-Protocol Analysis Set (PPAS)	All participants receiving at least one dose of reciferecept and have complete data at baseline through month 12 and without protocol deviations that were thought to impact the efficacy evaluation during the treatment period. Participants will be analyzed according to the randomized intervention.
PK Concentration set	All participants who received at least one dose of reciferecept and have at least one evaluable concentration.
PK Study Cohort	All participants who received a dose of the reciferecept Phase 2 formulation and a dose of the Phase 3 formulation with at least one evaluable concentration result.

Population	Description
PK Study Cohort Parameter (PKCP)	All participants in the PK cohort who have at least one PK parameter of interest.

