5.2.1. Analyses for Longitudinal Continuous Endpoints

Mixed-effect, repeated measures (MMRM) models will be used. The fixed effects of treatment, visit, treatment-by-visit interaction, age and gender will be included. Visit will be modeled as a categorical covariate. (If the model does not converge then Visit will be modeled as a continuous covariate.) Unstructured covariance matrix will be assumed for the model errors. Compound symmetry covariance matrix will be used if the model with unstructured variance covariance doesn't converge.

When modeling the change from baseline values, the variable for visit will start with the first post-baseline visit. At each visit, estimates of least square mean (LSM) values and the LSM differences between treatment groups will be derived from the model. The corresponding p-values and 95% confidence intervals will also be derived from the model.

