5.3.1. PK and Biomarker Data

Concentrations Below the Limit of Quantification

In all data presentations (except listings), concentrations below the limit of quantification (BLQ) will be set to zero. (In listings BLQ values will be reported as “<LLQ”, where LLQ will be replaced with the value for the lower limit of quantification). For population PK modeling, BLQ will be handled by the Pfizer standard processes.

Deviations, Missing Concentrations and Anomalous Values

In summary tables of concentration data by dose, visit day and time, statistics will be calculated having set concentrations to missing if 1 of the following cases is true:

A concentration has been collected as ND (ie not done) or NS (ie no sample),

A deviation in sampling time (15% beyond the sampling time window) is of sufficient concern or a concentration has been flagged anomalous by the pharmacokineticist.

Note that summary statistics will not be presented at a particular time point if more than 50% of the data are missing.

Pharmacokinetic Parameters

Nonlinear mixed effect modeling will be performed to evaluate pharmacokinetic parameters including clearance, area under the curve at steady state over the dosing interval for reciferecept. Additional details on the population PK modeling will be described in the population modeling analysis plan.

In summary tables, statistics will be calculated by setting NC values to missing; and statistics will be presented for a particular dose with ≥ 3 evaluable measurements.

If an individual subject has a known biased estimate of a PK parameter (due for example to an unexpected event such as dosing error), this will be footnoted in summary tables and will not be included in the calculation of summary statistics or statistical analyses.

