6. ANALYSES AND SUMMARIES

6.1. Primary Endpoint(s)

6.1.1. Increase in height growth above expected in reference population

6.1.1.1. Main Analysis

- Estimand strategy: Hypothetical ([Section 2.1.1](#)).
- Analysis set: FAS ([Section 4](#)).
- Analysis methodology: Change from baseline relative to Merker (2018) will be analyzed using MMRM including data from Months 3, 6, 9, and 12 with gender (and possibly age) as a covariate, subject (and/or time) as a random effect and an unstructured covariance matrix ([Section 5.2.1](#)).
- Intercurrent events and missing data: Data after study drug discontinuation and rescue will be excluded; intermediate missing values will not be imputed.
- The sample size, mean, standard deviation, median, minimum, and maximum at the baseline and postbaseline visits for observed standing height and change from baseline will be presented for each treatment arm.
- The least-squares (LS) means, the 95% confidence interval for the LS means, the difference between the LS means for each pair of treatment groups, and the corresponding 95% confidence interval will be presented for change from baseline in standing height for all postbaseline visits.

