Appendix 2.3. Definition of Protocol Deviations That Relate to Statistical Analyses/Populations

Appendix 3. Data Set Descriptions

Appendix 4. Statistical Methodology Details

Linear Interpolation

Linear interpolation will be employed to provide mean expected standing height values at 6 month interval for children $>$ age 4. The SAS code is as follows:

```
proc expand data=mydata out=LinInterp;
  convert exp_mean=linear / method=join;
  id age;
run;
```

MMRM

MMRM will be used for height growth and arm span-height difference. The SAS code is as follows:

```
proc mixed data=mydata;
  class dose gender month;
  model height = dose month gender age/s;
  random int month / type=un sub=subject;
  lsmean dose;
run;
```

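### The SAP's Month 12 window, the primary time point, closes one day after target, and no rule says how a later height is labelled

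*SAP*

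**What the plan says.** The reporting windows are in SAP Appendix 2.1, in the order target, start, end. The last row is "Month 12 Day 365 Day 346 Day 366". The row before it is "Month 11 Day 331 Day 316 Day 345". The table has no row for follow-up or early termination and no rule for a record that falls outside every window.

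The primary efficacy variable is height growth at 12 months (SAP 2.1.1). SAP 6.1.1.1 analyses it with "MMRM including data from Months 3, 6, 9, and 12". SAP 5.2.1 states "Visit will be modeled as a categorical covariate", with a continuous version only if the model does not converge. The code in SAP Appendix 4 agrees: "class dose gender month". Missing values are not imputed. The per-protocol set (SAP Section 4) requires that participants "have complete data at baseline through month 12".

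The protocol's SoA (Section 1.3) puts Month 12 at Day 365 and prints its visit window as 14 with no sign. Neighbouring visits show ±7.

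Protocol 9.4 says that the SAP "will describe the analyses and procedures for accounting for missing, unused, and spurious data". For PK concentrations the SAP does give a timing rule, in 5.3.1: "A deviation in sampling time (15% beyond the sampling time window) is of sufficient concern". It gives none for heights.

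**The concern.** The window for the primary time point is lopsided in a way that no other monthly window is. It accepts a height taken 19 days early and refuses one taken two days late. Because month is a categorical factor, the label decides whether a height counts as a Month 12 value at all.

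At stake are heights that were measured but would not contribute at the time point that matters. They would become missing values, the Month 12 estimate would be less precise, and on a literal reading of the completeness condition the child would also leave the per-protocol set. If instead the table is not meant to label efficacy visits, the rule that does so is not stated. It could then be chosen after the heights have been seen.

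**Working it through.** The SAP window is a listed boundary with no formula behind it, so there is no calculated figure to reproduce. The check is day arithmetic on the SAP table (Appendix 2.1) and the SoA (Protocol 1.3).

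**1. Offsets from the SAP target.**
- Month 12: start 346 - 365 = -19; end 366 - 365 = +1.
- Months 2 to 11: end minus target is 75 - 61 = 14, 105 - 91 = 14, and so on to 345 - 331 = 14. All ten end at +14.

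**2. Does each SAP window contain its SoA window?**
- Day 29: SoA 29 to 30, inside 20 to 39.
- Month 2: 61 ± 3 = 58 to 64, inside 40 to 75.
- Month 3: 91 ± 5 = 86 to 96, inside 76 to 105.
- Month 6: 183 ± 7 = 176 to 190, inside 166 to 195.
- Month 11: 333 ± 7 = 326 to 340, inside 316 to 345.
- The other rows from Screening to Month 10 behave the same way, so 16 of 16 rows before Month 12 are contained.

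**3. Month 12 against Days 346 to 366, for each possible sign of the SoA's 14.**

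| Reading | SoA days | Days permitted | Permitted but after Day 366 |
|---|---|---|---|
| ±14 | 351 to 379 | 29 | 13 (367 to 379) |
| +14 | 365 to 379 | 15 | 13 (367 to 379) |
| -14 | 351 to 365 | 15 | 0 |

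These are counts of calendar days, not of children. Under -14 a height after Day 366 is a late visit, and it still has no label in the table.

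**4. Size.** The documents give no distribution of visit dates, so the number of heights affected cannot be computed. Each affected child removes one of the 15 planned Month 12 values in a dose group: 1/15 = 6.7%. The child's Month 3, 6 and 9 heights stay in the full-analysis-set model.

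**5. Power.** Protocol 9.2 gives variability .15, an effect of 50% above reference and a one-sided level of 0.017, and claims over 90%. Taking .15 as an SD on the ratio scale (an assumption), one-sample t-test power is above 99.9% at n = 15 and at n = 6, and still 96% at n = 4.

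**6. Room to extend.** An end at +14 is Day 365 + 14 = 379. The follow-up window opens on 396 - 7 = Day 389, so 389 - 379 = 10 days remain.

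**7. Effect of timing on the endpoint.** H (SAP Appendix 2.2) divides observed by expected growth. Assume that expected growth is held at 12 months and that growth is linear, with baseline on Day 1. A Day 379 height then covers 378 days against 364: 378/364 = 1.038, so H rises by about 3.8%. A Day 346 height, already admitted, covers 345: 345/364 = 0.948, so H falls by about 5.2%.

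**The case against.** The strongest objection is that the clash with the SoA rests on a sign that cannot be seen. The sign may have been lost when the PDF was read, and that would not be an error in the plan. The SAP table itself leans somewhat towards -14: only that reading makes all 17 rows contain their SoA windows, and a window of -19/+1 suits a backward-only allowance. This stands. A reader might infer that the SAP plainly contradicts the SoA, but the documents do not establish that. What remains is the SAP's own boundary, which is legible and leaves any height after Day 366 unlabelled under every sign.

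Second, nothing says that the table decides which heights enter the model. Its title refers to reporting, and it omits early termination, where anthropometry is also scheduled. SAP Appendix 1 keeps all collected data in the main analysis whatever intercurrent events occur, and Protocol 6.3.2 says blinded and unblinded measurements are both analysed. These statements weigh against discarding a height, but none assigns it a month. The rule in SAP 6.6.3 on unplanned time points covers vital signs only. So the use of the table is unsettled, and the point has to be put conditionally.

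Third, membership of the analysis sets is fixed before unblinding and database release (SAP Section 4). That limits the post hoc worry for the per-protocol set. It does not settle the month label in the full-analysis-set model.

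Fourth, a later end day admits heights with slightly more growth time, which favours the drug. That is a real cost of up to about 3.8% under the stated assumptions. It is smaller than the opposite shift of about 5.2% that the present window already allows.

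**Conclusion.** The point holds in a limited form. The Month 12 window ends at +1 day where Months 2 to 11 end at +14, it is the last row, and the SAP has no out-of-window or nominal-visit rule for heights. If the table labels visits, heights after Day 366 are lost to the primary time point. They are on time under ±14 or +14 (Days 367 to 379) and late under -14.

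The harm is avoidable missing Month 12 data, at 6.7% of a dose group's 15 planned values per child, and a smaller per-protocol set if completeness is read literally.

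Two stronger readings are tempting and not supported:
- That 13 of 29 or 13 of 15 Month 12 heights would be lost. Those fractions are of permitted days, and visit dates are not given.
- That the trial loses its power. On the stated inputs, with .15 taken as an SD, power stays above 90% even at four children per dose.

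The conclusion assumes that the table is applied as printed, which the SAP does not expressly say. Minor priority.

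**What to change.** In SAP Appendix 2.1, set the Month 12 end day to Day 379. This matches the +14 of Months 2 to 11, covers the SoA window under any sign, and stops 10 days before follow-up opens. Confirm the sign of the SoA's Month 12 window and reconcile the two tables.

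Add one sentence saying whether the month label in the MMRM comes from this table or from the scheduled visit. Nothing further is needed. The SoA schedules a single Month 12 anthropometry, so no tie-break between heights is required, and an open-ended fallback to the nominal visit would remove any outer limit.

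The cost is one end day and one sentence, fixed before heights are reviewed, with no new data. The downside is the shift in H of up to about 3.8% for a Day 379 height under the assumptions above. The endpoint and the model do not change, so the amendment clauses for major modifications (Protocol Section 9, SAP Section 2) should not be triggered. A protocol clarification is needed only if the sign is also absent from the source SoA.

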Appendix 2.2. Endpoint Derivations

Height Growth

The primary efficacy endpoint is H defined by the following:

$$H_{ijkl} = \frac{Y_{ijkl} - Y_{i0kl}}{Z_{jl} - Z_{0l}},$$

where Y_{ijkl} is the observed standing height for the i th subject, at month j on dose k with gender factor l ($j=0$ denotes baseline measurement) and Z_{jl} is the mean expected standing height based on Merker for subject i 's age.

Mean expected standing height from Merker is sorted by 6 months up to age 4, while means expected values for children > 4 years are sorted per annum. Linear interpolation will be employed to calculate mean expected values so that mean standing height are sorted at 6 month intervals for children > 4 years. SAS code for the linear interpolation calculation will be provided in Appendix 4.

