7.2. Interim Analyses and Summaries

Height Growth & Arm span to height/length difference

- Estimand strategy: Hypothetical ([Section 2.1.1](#)).
- Analysis set: FAS ([Section 4](#)).
- Analysis methodology: Change from baseline relative to Merker (2018) will be analyzed using MMRM including data from Months 3 and 6, with gender as a covariate, subject (and/or time) as a random effect and an unstructured covariance matrix ([Section 5.2.1](#)).
- Intercurrent events and missing data: Data after study drug discontinuation and rescue will be excluded; intermediate missing values will not be imputed.
- The sample size, mean, standard deviation, median, minimum, and maximum at the baseline and postbaseline visits for observed standing height (and arm span to standing height difference) and change from baseline will be presented for each treatment arm.

The least-squares (LS) means, the 95% confidence interval for the LS means, the difference between the LS means for each pair of treatment groups, and the corresponding 95% confidence interval will be presented for change from baseline in standing height (and arm span to standing height difference) for all postbaseline visits.

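### The Appendix 4 code and Appendix 1 terms drop the treatment-by-visit interaction that SAP 5.2.1 requires, and the code averages over visits instead of estimating Month 12; the 6-month reference grid also lacks an exact-age rule

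*SAP*

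**What the plan says.** **Model.** SAP 2.1.1 sets the population summary as mean H at 12 months. SAP 5.2.1 lists treatment, visit, their interaction, age and gender as fixed effects, and asks for LS means at every visit. SAP 6.1.1.1 points to 5.2.1, analyses H "using MMRM including data from Months 3, 6, 9, and 12", and wants LS means for all post-baseline visits. SAP 7.2 does the same at the interim, "using MMRM including data from Months 3 and 6, with gender as a covariate".

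The Appendix 4 code, given for both height growth and the arm span difference, reads "model height = dose month gender age/s" and then requests only `lsmean dose`. Appendix 1 gives the main analysis as "MMRM with terms time,dose, gender & age", under an endpoint labelled as change to Month 12. Neither has a dose-by-time term.

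**Reference height.** Appendix 2.2 defines H = (Yj − Y0)/(Zj − Z0), where Y is observed height and Z is the reference mean for the child's age. The published reference "is sorted by 6 months up to age 4, while means expected values for children > 4 years are sorted per annum". Interpolation is used to "calculate mean expected values so that mean standing height are sorted at 6 month intervals for children > 4 years". Appendix 4 repeats this: "Linear interpolation will be employed to provide mean expected standing height values at 6 month interval for children" older than 4. The interpolation code names no target ages. Nothing is said about an age that falls between grid points, or about any interpolation between ages 2 and 4.

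**The concern.** The SAP gives two different models for a co-primary endpoint, and the one written out as code is the one that does not deliver the estimand. H is cumulative from baseline, so an effect that starts late or fades makes H differ between visits. A mean over visits then answers a different question from Month 12. A programmer who follows Appendix 4 would report that mean.

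The reference grid raises a separate, lesser question. Height is measured every 3 months but the reference steps every 6. If the grid served as a look-up table, some denominators would be zero or the wrong length. A zero denominator would be noticed, so the practical risk is that the rule for the denominator is settled once data are visible. Doses are open-label except to the anthropometrists, and an interim efficacy analysis is planned.

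**Working it through.** **1. The plan's own figure.** Protocol 9.2: 15 per dose, one-sided 0.05/3 = 0.0167 (stated as 0.017), variability 0.15, 50% growth above reference. Taking 0.15 as the SD of H (the scale is not stated), a one-sample t-test of mean H = 1 has noncentrality (0.5/0.15) × √15 = 12.9. Power exceeds 99.9%, so the stated lower bound of 90% is met.

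**2. What `lsmean dose` returns.** For a visit profile shared by all doses, the model without interaction gives the plain average of the visit means. The profiles below are assumed; each of the last two ends at 1.50.

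| Effect | Months 3, 6, 9, 12 | Appendix 4 output | Month 12 |
|---|---|---|---|
| Constant | 1.50, 1.50, 1.50, 1.50 | 1.50 | 1.50 |
| Starts after 3 months | 1.00, 1.33, 1.44, 1.50 | 5.27/4 = 1.32 | 1.50 |
| First 6 months only | 2.00, 2.00, 1.67, 1.50 | 7.17/4 = 1.79 | 1.50 |

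At the interim, the second profile gives (1.00 + 1.33)/2 = 1.17 against 1.33 at Month 6.

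**3. Asking for month means is not enough.** Assume profiles of 1, 1, 1, 1 (low), 1.0, 1.1, 1.2, 1.3 (medium) and 1.125, 1.25, 1.375, 1.5 (high), with complete data and visits weighted equally. The dose means are 1.00, 1.15 and 1.3125, and the grand mean is 1.154. The Month 12 mean over doses is (1.0 + 1.3 + 1.5)/3 = 1.267. The additive model's Month 12 value is the dose mean plus 1.267 − 1.154 = 0.1125, which gives 1.11, 1.26 and 1.43 against true values of 1.0, 1.3 and 1.5. The inactive low dose appears to work. The interaction term itself has to be restored.

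**4. The grid used as a look-up (conditional).** Assume baseline ages spread evenly and reference growth locally linear. At nominal months, for a child growing at reference (true H = 1):

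- Month 3: 3/6 = 50% cross no grid point, so the denominator is zero; the rest have H = 3/6 = 0.5.
- Month 6: 6/6 = 1.
- Month 9: half have 9/6 = 1.5 and half have 9/12 = 0.75.
- Month 12: 12/12 = 1.

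With actual dates, Month 12 depends on timing. Half a year is 182.6 days.

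- Target Day 365, Day 1 baseline: 364 days elapse, and (365.25 − 364)/182.6 = 0.7% get a 6-month denominator. Mean 0.99–1.00, total SD 0.17.
- Visits even over Day 346–366 (the window in SAP Appendix 2.1), Day 1 baseline: on average 355 days elapse, and (365.25 − 355)/182.6 = 5.6% get a 6-month denominator, with H about 1.92 against 0.97 for the others. Mean 1.01–1.03. Artefact SD is about 0.22, and total SD is about √(0.22² + 0.15² × 1.10) = 0.27, where 1.10 is the mean square of the distorted H.
- Same window, with baseline height taken at screening as in SAP 3.4 (Day −14 to −1): 2.5% get a 6-month and 1.0% an 18-month denominator; total SD about 0.22.
- Target day with the screening baseline: total SD about 0.16.
- Nominal months: total SD stays at 0.15.

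At the worst of these (SD 0.27), testing Month 12 alone with 15 per dose, simulated rejection with a look-up against exact age is 100% against 100% at true H 1.5, 90% against 99.5% at 1.2, 26% against 59% at 1.1, and 0.3% against 1.7% at 1.0.

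**5. Exact-age interpolation.** Denominators become 3, 6, 9 and 12 months of growth, and the distortion in step 4 disappears. The error in step 2 remains, because the two points are independent.

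**The case against.** On the model, the SAP body is right. Section 5.2.1 has the interaction and by-visit LS means, 6.1.1.1 and 7.2 rely on it, and Appendix 1 labels its endpoint as Month 12. A reader might infer that no Month 12 analysis is planned, or that Appendix 1 itself yields a visit average. Neither follows: the Month 12 analysis is in the body, and Appendix 1 only lists terms. The 1.32 and 1.79 also come from assumed profiles. What stands is the contradiction. The explicit code does not produce what the body requires.

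On the grid, the objection carries more weight. Z is defined for the child's age, linear interpolation is the only tool named, the code could be run at exact ages, and rounding is nowhere mentioned. A look-up would expose itself through zero denominators. A reader might infer that the primary result is biased, that Month 12 variability nearly doubles, or that the power claim fails. The documents do not support these: the Month 12 mean is about right, the SD of 0.27 is one end of a range that starts at no change, and power at a 50% gain is unaffected. Larger biases in the dose means would need a look-up, zero denominators set to missing and the Appendix 4 output, all together. What stands is that the rule is unstated.

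The interim cannot stop the study or change its size (SAP 7.1), which limits the consequences of either point there.

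**Conclusion.** The main point holds on the text alone: Appendix 4 and Appendix 1 omit an interaction that 5.2.1 requires, and the code as written does not estimate the Month 12 estimand or the by-visit means. The error is nil for a constant effect. In the two assumed profiles it is 1.32 − 1.50 = −0.18 and 1.79 − 1.50 = +0.29 on the scale of H.

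The secondary point is a gap in the derivation of H. Under a look-up, about half of Month 3 values are undefined and the rest about half the true value, and Month 9 values are about 1.5 or 0.75 times true. The Month 12 mean is within about 3%, and total SD is 0.16–0.27 against 0.15, or unchanged with nominal months. These figures rest on evenly spread ages, assumed reference velocities (constant or declining with age), and 0.15 being the SD of H; the reference table is not in the documents. No planned decision at the designed 50% gain changes. Both points should be fixed before the analysis.

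**What to change.** 1. In Appendix 4, fit H = dose month dose*month gender age and output the dose-by-month LS means. Name Month 12 as the primary estimate (Month 6 at the interim). Make the same change for the arm span difference, and add the interaction to the Appendix 1 terms.
2. In Appendix 2.2, replace the 6-month table with linear interpolation of the sex-specific reference mean to each child's exact age on the date of the baseline height and of every post-baseline height, at all ages including 2 to 4.
3. As clarifications, index Z by child, and state a convention for cases where only month and year of birth are held, which Protocol Section 8 allows.

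The cost is a few lines of SAP text and code before the analysis, with no new data, visits or burden on participants.
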